#### REPORTING PROTOCOL DEVIATIONS

All protocol deviations must be reported using the Protocol Deviations CRF. Note that a protocol deviation that is also an AE should be reported as an AE rather than a deviation.

#### Reasons for deviation:

- Informed Consent not obtained/signed/dated
- o Incorrect version of Informed Consent obtained/signed/dated
- o Eligibility Criteria not met
- o Randomization not performed as required
- o Not all required testing/assessments completed
- o Follow-up visit/testing/assessments done outside of visit window
- o Follow-up visit not done/missed
- o SAE submitted to Sponsor and/or EC outside the required timeframe
- Not all required testing/assessments completed and follow-up visit/testing/assessments done outside of visit window

#### 10.2 ADVERSE EVENTS AND UNANTICIPATED PROBLEMS

Ad adverse event is considered "unexpected" if it is not listed in the protocol, or Informed Consent Forms or is not listed at the specificity, severity or rate of occurrence that has been observed; or, is not consistent with the risk information described in the general investigational plan or elsewhere.

#### ADVERSE EVENTS

An AE is any unfavorable or unintended sign, symptom or disease occurring in a participant at any stage of the study, whether or not considered related to the study.

#### CLINICAL ENDPOINTS

Any reported AEs that meet the following are also clinical endpoints and will be reported on the End of Study form. DMC Project Manager will review all AEs to determine if they also meet

clinical endpoint criteria. If criteria are met, the DMC Project Manager will ensure all documentation need for endpoint review is received by the site study coordinator.

	Anticipated A	Adverse Events (AAE)	Unanticipated Adverse Events (UAE)			
	
 
Headaches
 
	
 
Oxygen saturation less
 
	
 
Any Adverse effect
 
	
 
Any event that
 
		
	o Fever	than 90 during the	on the health or	results in death		
	o Chills	monitoring period	safety caused by, or	o Conversion of		
	
 
Loss of appetite
 
	
 
Absolute reduction in
 
	associated with, the	family members		
	o Nausea	oxygen saturation of more	CPAP or progression	to COVID		
	
 
Vomiting
 
	than 4% associated with	of underlying COVID	positive in the		
	o Fatigue	shortness of breath or	that was not	CPAP group		
	
 
Muscle or body aches
 
	difficulty breathing	previously identified			
	
 
New loss of taste or smell
 
	o Persistent pain or pressure	in the product			
	
 
Sore throat
 
	in the chest	labeling, published			
	
 
Congestion or runny nose
 
	
 
Any worsening of COVID
 
	literature or study			
	
 
Diarrhea
 
	symptoms that lead to an	protocol			
	
 
Decrease in oxygen
 
	Emergency room visit,				
	saturation (that is not	hospital admission, ICU				
	associated with shortness	admission, intubation, or				
	of breath or difficulty	mechanical ventilation				
	breathing)					
Reporting	None	Redcap	None	Redcap, DSMB, IRB		

#### 10.5 DISCONTINUATION

#### DISCONTINUATION – TREATMENT STOP/DISCONTINUATION

Participants may require additional/alternative therapies that may or may not be exclusionary criteria and are designed to minimize the potential risks to participant's safety which can result in discontinuation of the study treatment. Discontinuation can be observed during either routine interim follow-up phone calls or visits, or as a result of study contact by the participant or the participant's physician. If the participant is deemed a 'discontinuation – treatment stop', the Treatment Stop CRF must be completed, arrangements for the return of the concentrator must be made, and the participant should still be followed-up per protocol, despite no longer receiving the study intervention, if agreed. Discontinuation – treatment stop in PAP-COVID are defined as follows:

• The participant's physician has identified a change in signs or symptoms that in his/her opinion are related to ongoing symptoms of COVID-19 and therefore warrant alternative treatment, such as permanent supplemental oxygen

#### 10.6 SURVEILLANCE

At each contact with the participant, the investigator must seek information on AEs, clinical endpoints, and urgent medical referrals. Information on all events/problems should be recorded immediately. All events/problems occurring during the study period must be recorded and reported. The clinical course of each event should be followed until resolution, stabilization, or until it has been determined that the study treatment or participation is not the cause and the event is not a defined clinical endpoint. Monitoring events/problems is a constant task given to all study personnel, and should be accomplished using all available sources, including (but not limited to):

- Spontaneous reports by the participant;
- Observations by key study personnel;
- o Reports to study staff by the participant or medical care providers;
- o Possible AE documented in records or progress notes.

In addition to receiving reports of potential AEs, the study coordinator should develop and implement a plan to monitor for AEs consistently and routinely through proactive measures such as:

- o Review participant's records for additional information;
- o Communicate with participant's medical providers if necessary.

In addition to these avenues of monitoring, AEs will be monitored more formally through several means of surveillance, including:

- At each follow-up visit, data will be collected that includes assessment of interim symptoms, concomitant medication use and any new illnesses or conditions that have occurred from the time of the previous visit.
- Research data will be interrogated to identify whether any questionnaire data exceed values that indicate an abnormality.

#### 10.7 REPORTING ADVERSE EVENTS

#### HOW TO REPORT AN ADVERSE EVENT

In response to an adverse event, the research coordinator must fill out the Adverse Event Case Report Form and notify the PI. The PI will provide further instructions on a case-by-case basis.

#### 10.8 FOLLOW-UP OF ADVERSE EVENTS

#### **DURING THE STUDY**

We will obtain signatures on a medical release form at enrollment, and then obtain any medical records throughout the duration of the patient's experience of the adverse events. We will be regularly checking in with the patient and appropriately documenting all progress until the adverse event has been resolved.

## 11 – DATA MANAGEMENT

#### 11.1 REDCAP

We will store all data collected from forms on RedCAP.

#### 11.2 ONCORE

All participant data will be stored on OnCore Clinical Trial Management Software.

#### 11.3 RIPPLE

All patient data for those who are ineligible or declined to participate will be stored in ripple.

#### 11.4 ENCOREEVERYWHERE

All CPAP monitoring and compliance/adherence data will be stored on EncoreEverywhere.

#### 11.5 CLOUDPAT

All sleep data will be stored on CloudPAT for the DMC to download and interpret.

#### 12 – QUALITY ASSURANCE

#### 12.1 QUALITY ASSURANCE PROCEDURES AND RESPONSIBILITIES

Quality control measures will be implemented at several levels to ensure that all centers and personnel meet and maintain comparable high levels of technical performance. Quality control will be optimized by multiple levels of training, monitoring, and feedback activities including coordinator training and certification of personnel for all specialized testing and monitoring procedures.

#### **COORDINATOR TRAINING**

After protocol and Manual of Procedures development, a training session will be held virtually on Zoom. Attendees will include study investigators, study coordinators, as well as the leaders of each subcommittee. Joint introductory sessions will be held that include a review of the entire protocol and study organization and allow study personnel to become acquainted. Specifically, but not exclusively, this training will ensure that all personnel understand the study's goals and objectives, as well as PAP-COVID specific data collection and procedures, to ensure that the study is conducted appropriately. Breakout sessions will focus on specific aspects of data collection and database management; anthropometry; AE monitoring and reporting; recruitment and retention; and data entry and data management. Some sessions will be audio-recorded and/or videotaped for future references by staff. Time will be allotted to document proficiency in specific procedures, which may require combinations of observation by the trainer and written exams. In addition to the initial coordinator training, ongoing training of study staff will be conducted. This training, in the form of conference calls, is designed to maintain a current level of project knowledge regarding developments taking place after the initial coordinator training.

#### 12.2 DATA INTEGRITY

#### **INSPECTIONS AND AUDITS**

Participation as an investigator in this study implies acceptance of potential inspection by applicable Institutional compliance and quality assurance offices. The investigator will permit study-related monitoring, audits, and inspections by the IRB, and Mount Sinai compliance and quality assurance groups of all study-related documents (e.g. source documents, regulatory documents, data collection instruments). The investigator will ensure the capability for inspections of applicable study-related facilities.

#### Database and Systems Management

The PI will routinely monitor data entered by the coordinators. The DMC and statisticians will check for data quality.

#### DATA RECOVERY

We will routinely backup the RedCAP databases so we have physical copies of the data.

#### 13 – REGULATORY COMPLIANCE

#### 13.1 RECORD KEEPING AND SOURCE DOCUMENTS

Source data consists of all information, original records of clinical findings, observations, or other activities in a clinical trial necessary for the reconstruction and evaluation of the trial. Source data are contained in source documents. Examples of these original (source) documents and data records include:

- Hospital records;
- Clinical and office charts;
- Laboratory notes;
- Evaluation checklists;
- Pharmacy records;
- Death records;
- Recorded data from automated instruments;
- Copies or transcriptions certified after verification as being accurate and complete;
- Photographic negatives;
- Digital pictures;
- Microfilm or magnetic media;
- X-rays;

All patient information will remain in OnCore and RedCAP.

#### RECORD RETENTION

It is the investigator's responsibility to retain essential study documents for at least seven years after the study is discontinued.

#### 13.2 INSTITUTIONAL REVIEW BOARD

It is the responsibility of the Principal Investigator (PI) to work with the IRB in initiating protocol approval and re-approval, notification of protocol and/or ICF changes, AEs, and termination of the study according to the appropriate IRB requirements.

#### 13.3 CONTINUING REVIEWS

The study is expected to last less than one year, and before any continuing reviewing will be needed. In the event that we need to extend the study, a continuing review will be submitted in accordance with Mount Sinai's IRB policies.

## **APPENDICES**

## FORMS

## SCREENING FORM

## **Screening Form**

1.	Source of participant's referral? (check one)
	Mount Sinai Main ED
	Mount Sinai ED Surge Space
	ED Precision Recovery Program
	□ EPIC
	□ other means, specify:
Demo	graphics and Subject History Form :
2.	Patient's demographic information was obtained via:  ☐ Chart Abstraction ☐ Oral Interview
3.	participant's current age?
4.	What is the participant's biological sex?  ☐ Male ☐ Female
5.	What is the participant's race (check all that apply)?
	American Indian or Alaska Native
	Asian
	Black or African American
	White or Caucasian
	Native Hawaiian or Other Pacific Islander
	Other (please specify):
	Unknown or Not Reported
6.	What is the participant's ethnicity?
	Hispanic or Latino
	Not Hispanic or Latino
7.	What is participant's BMI?

## **Enrollment Eligibility Form:**

## **ER Admission Data Form**

*This is abstracted from the chart, data from the date of their admission to the ER prior to baseline
1. Date of admission to the ER:
2. Time of admission to the ER:
3. Number of days since symptom onset:
4. Source of COVID infection:

□ Unknown

□ Known

□ Occupational

□ Household
□ Other:
5. Did patient have any of the following symptoms (y/n):    Fever (y/n)   Cough (y/n)   Shortness of breath (y/n)   Chest tightness (y/n)   Sputum (y/n)   Nasal congestion (y/n)   Sore throat (y/n)   Chills (y/n)   gastrointestinal symptoms (y/n)
Vital signs in the ED
6. Temperature Fahrenheit:
7. Oxygen saturation:
□ Without supplemental oxygen
□ With supplemental oxygen
☐ How much supplemental oxygen?
☐ What method of oxygen: nasal canula, face mask, high flow nasal canula
8. Blood pressure:/
9. Pulse:

## VISITS FIGURE

## VISITS FIGURE

	Visit 1	Visit 2 Equipment Set Up Call	6-12 hrs	18-24 hrs	30-36 hrs	42-48 hrs	54-60 hrs	66-72 hrs	Daily Days 4-7 (CPAP only)	Daily Days 4-7 (no CPAP)	Everyone Days 8-14, 28	Event Driven
Phone consent with witness (Consent Form)	√											
Screening	✓											
Enrollment Eligibility Form	√											
ER Admission Data Form	√											
Demographics and Subject History Form	√											
Participant Contact Form	√											
Medications Form	✓											
CPAP and WatchPat Assignment Form	√											
PROMIS questionnaire Form	√											
Randomization Form	✓											
CPAP Set up Form		✓										

T			1	1		1		T			
WatchPAT and Pox Set up Form		√									
Follow-up Questionnaire			✓	✓	✓	√	✓	✓	✓		
Respiratory Questionnaire Form	✓		✓	✓	✓	√	✓	✓	✓	✓	
CPAP Adherence Form (Downloaded)			✓	√	√	√	√	✓			
CPAP Use Form (For Patient)			✓	√	√	√	√	✓			
WatchPAT Download Form											
Adverse Event Report Form											√
Discontinuation Form											√
Interval Assessment Form										✓	
Protocol Deviation/Violation											√
End of Study Form											√
Investigator Statement Form (Day 28)										✓

Early Continuous Positive Airway Pressure (CPAP) in COVID-19 Confirmed or Suspected Patients

PI: [name], MPH

NCT04390191

Document Date: 4-21-2020

General Design Issues

This is a prospective, single-center, parallel group, open-label, randomized clinical trial. The primary objective is to evaluate the efficacy and safety of the use of CPAP versus control in COVID-19 suspected or confirmed patients with pneumonia or respiratory illness. The primary efficacy endpoint is a **non-weighted composite endpoint comprised of the following components:**

- All-cause mortality within 14 days of randomization
- Hospital Admission (including ED visit) within 14 days of randomization
- Oxygen saturation less than 90 during the 72-hour observation period from randomization
- Absolute reduction in oxygen saturation of more than 4% during the 72-hour observation period from randomization

Sample Size and Power

Sample size was restricted by the availability of CPAP and the need for rapid answers during the exceptional health care challenges and fluid epidemiological conditions. The table below summarizes the effect sizes (% reduction in the proportion of patients with a negative outcome) that can be detected with sufficient power (>80%) under several scenarios assuming a total sample size of 200 patients (100 per arm) using a two-sided Fisher's exact test at the 0.05 significance level. Preliminary data from the Mount Sinai Health System indicated that about 25% of the COVID-19 positive patients with respiratory distress were sent home and subsequently hospitalized. We assumed that the proportion of patients with a negative outcome in the control group will range between 25% to 50%. Depending on these values, the planned sample size will allow us to detect a relative treatment reduction between 64% to 42% in this range (see table below).

Furthermore, given the short follow-up time for the assessment of the primary outcome and the nature of the primary outcome, we anticipate that we will be able to assess the primary outcome on all patients. We also believe that patients will be supportive of this intervention and compliant with treatment, so sample size was not adjusted for drop-out rates. However, if due to unforeseen circumstances we will conservatively set any missing primary outcome assessment to "negative" or "failure". Power calculations were performed in SAS 9.4 using the PROC POWER function.

Proportion of patients with Negative outcome	Control	0.25	0.30	0.35	0.4	0.45	0.5
	СРАР	0.09	0.12	0.16	0.20	0.25	0.29
	Relative reduction in CPAP arm (%)	64	60	54	50	44	42

Randomization Design and Procedure

Patients will be randomized using a 1:1 allocation to CPAP versus control group. The randomization will be stratified by BMI ($\geq=30$ and ≤30), gender and age (≤60 , $\geq=60$). A random permuted block design will be employed, with random blocks of size 2 and 4.

Data Monitoring and Analysis

Primary Efficacy Analysis

The primary efficacy endpoint is the proportion of patients with a negative composite endpoint within 14 days of randomization and will be compared between CPAP and control groups. The null hypothesis is that the proportion of patients with a negative outcome will be the same between patients randomized to CPAP versus control arm. This hypothesis will be tested using a two-sided Fisher's exact test at 0.05 alpha level. The primary analysis will be conducted according to the intention-to-treat principle.

Early stopping rule: If three deaths are observed in the CPAP group, enrollment will be halted pending DSMB review and recommendations. As of April 03, the death rate for COVID-19 positive patients in NYC was 2.99% [95% Clopper Pearson CI= 2.986, 2.997]. The rate is expected to be lower for our patient population. As such, 3 deaths among 100 patients will indicate a proportion of 3% [95% CI: 2.57%, 3.78%].

Analyses of Secondary Endpoints

Safety

Safety analyses will be conducted according to randomization assignment and treatment actually received. Adverse event rates will be calculated as the ratio of the total number of events over 14 days divided by total patient-days at risk for the specific event from randomization. A Poisson model with robust variance estimation will be used to compare SAEs between CPAP and control patients.

Time-to-events outcomes

Time from randomization to event outcomes (Hospitalization or ED visit, ICU admission, intubation and mechanical ventilation) within 14 days of randomization will be compared between randomization groups using a log-rank test or Gray's test in the presence of competing risk of death. In addition, survival at days 14 and 28 post-randomization will be described by Kaplan-Meier curves and a log-rank test will be used to compare survival between the two groups.

Respiratory Function

- Improvement in oxygen saturation will be compared between randomization groups using linear mixed-effect models with patient as a random effect.
- Improvement in respiratory symptoms, as measured by the Clinical COPD Questionnaire, will be compared between randomization groups using linear mixed-effect models with patient as a random effect.

Conversion rate of family members

The conversion rates (yes/no) of family members in the two randomization groups will be compared using a Fisher's exact test. If there is sufficient variability, a zero-inflated count model may be considered as well.

Continuation of CPAP for greater than 72 hours

The proportion of patients in the CPAP group who elected to continue CPAP use after 72 hours will be estimated along with 95% Coppler-Pearson confidence intervals.

Exploratory Analyses

Exploratory analyses will be conducted similarly as the primary analysis except that it will be only in the control arm comparing OSA versus non-OSA patents and obese vs non-obese patients.

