#### **OBJECTIVES**

Aim 1: Given the expected shortage of ventilators to treat COVID-19 suspected or confirmed individuals with severe acute respiratory distress syndrome (SARS)/ARDS, we propose a prospective, single-center, parallel group, open label, randomized clinical trial of CPAP (n=100) vs. control (n=100) in COVID-19 suspected or confirmed patients with abnormal chest x-ray or respiratory symptoms. The overarching aim of this proposal is to determine if early use of CPAP at home reduces the need for hospitalization admission or death in COVID-19 suspected or confirmed patients. We will include adult patients (age>18), oversampling when possible for obese patients who live alone or have more than one bedroom at home, with serologically confirmed or under investigation for acute COVID-19 infection, who have one or more of the following: fever (>38°C), sore throat, myalgia or flu-like illness AND have one or more of the following additional symptom or diagnostic criteria: abnormal chest x-ray, new onset cough, mild hypoxemia at rest (saturation less than 96%), abnormal lung exam, chest tightness or shortness of breath AND who are without need for hospital admission, i.e. being sent home. Patients with preexisting pulmonary diseases such as advanced COPD, advanced parenchymal lung disease, history of pneumothorax etc. will be excluded (see inclusion and exclusion criteria for more information). Participants in both arms will be shipped a pulse oximeter to monitor oxygen saturation and a disposable home sleep apnea monitor (WatchPAT) to track blood oxygen level continuously for 12 hours with data feed into a cloud based platform. Additionally, patients in the treatment arm (n=100) will be randomized to receive CPAP at fixed pressure: 8 cm water pressure in women and 10cm water pressure in men. All obese patients (BMI>=30) will be treated with a fixed pressure of 10cm of water pressure (both men and women). The CPAP pressure will be adjusted based on patient's comfort but will not deviate from the range of 8-10cm noted above. The treatment will be prescribed for 72 hours continuously (except for daily activities such as eating, grooming etc). While the study protocol will end at 72 hours, patients who wish to continue CPAP will be allowed to do so for symptomatic benefit up to 7 days. All CPAP recipients will be given a full-face mask and will be asked to stay in quarantine for the duration of the protocol to avoid risk of infecting family members with aerosol. We hypothesize that initiation of early CPAP in COVID infected patients with respiratory abnormalities will decrease the risk of subsequent hospitalization or death in 14 days from randomization. Patients will be followed for 28 days and as a secondary endpoint we will assess 28 day mortality as well as to assess for late impact of CPAP.

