#### **ENDPOINTS**

#### **Primary endpoint:**

The primary efficacy endpoint is a non-weighted composite endpoint comprised of the following components;

- All-cause mortality within 14 days of randomization
- Hospital Admission (including ED visit) within 14 days of randomization
- Oxygen saturation less than 90 during the 72-hour observation period from randomization
- Absolute reduction in oxygen saturation of more than 4% during the 72-hour observation period from randomization

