#### 7.1 VISIT SCHEDULE

#### Study Procedures:

- 1) Patients will be screened as described earlier
- 2) Eligible patients will be provided a flyer by ED provider when possible but may also be contacted by telephone once they have been discharged. (Of note: we are being approached by patients who are discharged from the hospital with COVID pneumonia who continue to experience shortness of breath and are requesting a CPAP without having prior knowledge of this study).
- 3) Research will be introduced to the patient, and if they agree to participate, a telephone consent will be conducted (according to IRB requirements including witness). Once patients have enrolled in the study, their PMD will also be notified of their participation. The patient will also be added to the study on EPIC, so that all treating physicians are aware of the patient's participation in our study.
- 4) Once patients have enrolled in the study, a pulse oximeter and a disposable WatchPAT One device will be mailed to the patients (within 24-48 hours of discharge). Orders placed before noon will be delivered the same day by a local durable medical equipment company we are working with. Orders placed past noon, CPAP delivery will be done the subsequent day or upto 48 hours if outside the New York area. Patients who are randomized to the treatment arm will receive a CPAP machine and three full-face masks in addition to the above noted equipment.
- 5) Patient will then be instructed via facetime or other video platform on CPAP setup and use, face mask fitting (those randomized to CPAP), and use of the WatchPAT One and pulse oximeter (for both CPAP and control arm). All participants will wear the WatchPAT one for one night whereas the oximeter will stay on continuously and the patient will report the saturation to us via follow up survey.
- 6) Patients randomized to receive CPAP will be asked to stay in isolation throughout the duration of the study i.e. 72 hours. They will be required to stay in a different room with the door shut and windows open (weather permitting). We will also ask the patient to stop using CPAP during meals or other daily activities. Subjects not on CPAP machine will also be instructed to sleep in a room with windows open (weather permitting).
- 7) Patients will use the CPAP machine as instructed for 72 hours.

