- 8) All patients will be contacted every 6-12 hours to complete follow up assessments. These follow ups will be done via a phone call. If the timing of these follow ups fall between 10pm-6am, the follow up will be deferred until after 6am. After 72 hours, all patients will then be contacted daily until day 14 from randomization. After day 14, research staff will continue to monitor the medical charts for any visits to the hospital. One last contact will be made on day 28.
- 9) After 72 hours, patients will be asked to discontinue using the CPAP and pulse oximeter. If patients wish to continue to use the CPAP, they may do so for up to 7 days from time of randomization.
- 10) The research staff will continue to call all patients daily (after the 72 hour mark) to assess symptoms.
- 11) The patients can also choose to monitor their oxygen saturation beyond the 72 hours of treatment.
- 12) CPAP download is available continuously however we will download data on usage, pressure, leak daily and make adjustments to the mask or CPAP pressure as needed for patient comfort. For patients experiencing significant trouble tolerating high pressure, we will decrease CPAP from 8-10 cm to a fixed CPAP of 5 cm for 2-4 hours after which we will raise it back to 8-10cm for the

- duration of the study. If the patient is not able to tolerate the pressure again, we will reduce it back to 5cm of water pressure for several hours before increasing the pressure. This will be continued until the patient withdraws or 72 hours are completed, whichever occurs first.
- 13) Patients will be asked to track their own oxygen saturation using the provided pulse oximeter and report it when we contact them for the 6-12 hour follow up calls/surveys.
- 14) The sleep apnea test will provide continuous oxygen and breathing data for a period of 12 hours during the 72 hours and will also provide information on oxygen saturation while the patient is asleep.

The outline of the forms that correspond to the study visits can be found in the Appendix, Figure 1. All of these forms are subsequently included in the following appendicies.

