#### SCREENING VISIT

Upon reaching out to patient, the coordinator will confirm enrollment eligibility with the patient prior to consenting.

#### 7.3 VISIT 1

Visit 1 is performed by the coordinator. It consists of the following forms:

- Phone consent
- Enrollment Eligibility Form
- ER Admission Data Form
- Demographics and Subject History Form
- Participant Contact Form
- Medications Form
- CPAP and WatchPAT Assignment Form
- PROMIS questionnaire Form
- Randomization Form
- Respiratory Questionnaire Form
- 1. Once the Mount Sinai team has randomized patient, we will email [contact] with demographics and equipment ordered.
- 2. Community surgical will call patient to confirm address and information, they will then initialize the WatchPAT.
- 3. The pin used will be the DOB in the following format: MMDD
- 4. The pin will be written on the WatchPAT box as well
- 5. Community surgical will then deliver the equipment box to the patient. Patient will receive documents to sign via docusign.

- 6. Once delivery has been made, community surgical will notify PI
- 7. Community surgical will register patient on encoreanywhere once patient has been registered it will take approximately 24 hours before we are able to see the patient on our end

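### The two oxygen-saturation components of the primary endpoint have no reference value for the >4% fall and no limit on which readings count; separately, Aim 2's independent effects cannot come from the planned unadjusted comparisons

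*SAP*

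**What the plan says.** **Endpoint.** SAP General Design Issues and Protocol 1.3 give the same two saturation components: "Oxygen saturation less than 90 during the 72-hour observation period from randomization" and "Absolute reduction in oxygen saturation of more than 4% during the 72-hour observation period from randomization". Each has a threshold and a window. Neither names a device, a reading (current, lowest or averaged) or, for the fall, a starting value.

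**Where saturation is collected.** Protocol 7.1 describes two sources in both arms.
- Pulse oximeter: WatchPAT is worn for one night, "whereas the oximeter will stay on continuously and the patient will report the saturation to us via follow up survey". Patients report values at calls every 6 to 12 hours. For calls due between 10pm and 6am, "the follow up will be deferred until after 6am".
- WatchPAT: Protocol 1.2 (Aim 1) gives its purpose as "to track blood oxygen level continuously for 12 hours with data feed into a cloud based platform". Protocol 7.1 item 14 places the recording within the 72 hours and says that it "will also provide information on oxygen saturation while the patient is asleep".

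**Possible reference.** The equipment is ordered "Once the Mount Sinai team has randomized patient" (Protocol 7.3), and delivery can take up to 48 hours (7.1 item 4). The only earlier saturation on a form that is shown is in the ER Admission Data Form: "This is abstracted from the chart, data from the date of their admission to the ER prior to baseline". That form allows the value to have been taken on supplemental oxygen.

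**A variant.** The adverse-event table in Protocol 10.2, under Clinical Endpoints, lists the >4% fall together with breathing symptoms. The primary component has no such condition.

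**Aim 2.** Protocol 1.2 expects OSA and obesity to be correlated and undertakes to determine the independent impact of each on the primary endpoint. SAP Exploratory Analyses repeats the primary method in the control arm, once for OSA and once for obesity.

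**The concern.** A composite is scored patient by patient. If the reference and the admissible readings are not fixed in advance, the same patient can be a success or a failure depending on choices made later. Because the trial is open-label, those choices could be made with the arm known.

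The unrestricted wording also admits readings taken during sleep. Protocol 1.2 (Aim 2) says that OSA is present in over half of obese people and that CPAP is its primary treatment, and the trial oversamples obese patients when possible. Counted sleep dips could therefore be commoner in controls than on CPAP for reasons unrelated to progression of COVID-19. The stated hypothesis is fewer hospitalizations or deaths within 14 days.

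For Aim 2, when two risk factors are correlated, an unadjusted comparison on one picks up the effect of the other.

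**Working it through.** **1. The plan's own power figures.** Exact power of the two-sided Fisher test at 0.05 with 100 per arm, for the SAP's six control/CPAP pairs (0.25/0.09 to 0.50/0.29), is 0.830, 0.854, 0.843, 0.844, 0.809 and 0.833. All exceed 80%, as the SAP states. The arithmetic is sound; what is open is the event behind the rates. The 25% comes from later hospitalization, and no saturation event rate is given.

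**2. Effect of the reference (documents' figures only).** In whole percents, a fall of more than 4 means reading ≤ reference − 5. Readings of 90 or above that fail only through this component are:

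| Reference | Extra failing readings |
|---|---|
| 92–94 | none |
| 95 | 90 |
| 96 | 90–91 |
| 97 | 90–92 |
| 98 | 90–93 |

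A reading of 92 fails when 92 ≤ reference − 5, that is, at a reference of 97 or more. The mild-hypoxemia criterion in Protocol 5.2 is 92–96, but patients can qualify on other criteria with higher values, and an ER value on oxygen may also be higher.

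**3. Readings available.** The Visits Figure has six check-in windows to 72 hours: 6-12, 18-24, 30-36, 42-48, 54-60 and 66-72. If the check-in clock starts at randomization and equipment arrives 48 hours later, four windows have passed and two remain. SAP Sample Size and Power sets a missing primary outcome to failure and does not say whether an empty window counts as missing.

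**4. If sleep dips were counted (assumed inputs, illustration only).** Assume a 25% rate from other causes in both arms, 40% obese, and OSA in 50% of the obese and in no others, so the OSA share is 0.40 × 0.50 = 0.20. Let c be the proportion of OSA patients with a counted dip and r the fraction of dips remaining on CPAP. Control rate = 0.25 + 0.75 × 0.20 × c; CPAP rate = 0.25 + 0.75 × 0.20 × c × r. Exact probability of Fisher significance favouring CPAP:

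| c | r = 0.2 | r = 0.5 |
|---|---|---|
| 0 | 1.7% | 1.7% |
| 0.25 | 5.0% | 3.4% |
| 0.5 | 11.8% | 6.2% |
| 1 | 37.3% | 15.5% |

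At c = 1 and r = 0.2 the rates are 40% v 28%. With an OSA share of 0.10 instead, 37.3% becomes 11.8% and 11.8% becomes 5.0%.

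**5. Aim 2 (assumed inputs).** Take 100 controls: 40 obese (20 with OSA) and 60 non-obese (6 with OSA). Failure is 40% in the obese and 15% in others, and OSA has no effect.
- OSA: (20 × 0.40 + 6 × 0.15)/26 = 34.2%.
- No OSA: (20 × 0.40 + 54 × 0.15)/74 = 21.8%.
- A significant OSA excess appears in 20.0% of trials, against 2.0% if every cell is 25%. With OSA in 0% to 20% of the non-obese, the range is 35.8% to 10.6%. With failure of 30% v 20% by obesity, 20.0% falls to 6.0%.
- Entering both factors in a logistic model gives a standard error of 0.569 for the OSA log odds ratio, so the 95% CI at a true odds ratio of 1 is exp(±1.96 × 0.569) = 0.33 to 3.05, on 40 × 0.40 + 60 × 0.15 = 25 expected events.

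**The case against.** **The source is described.** Protocol 7.1 items 5 and 13 set out one operational route in both arms: oximeter values reported at calls. WatchPAT is called the sleep apnea test and serves Aim 2. No text sends its data to the primary endpoint. This stands, and it rules out a tempting stronger reading, that the plan scores WatchPAT data or is biased towards CPAP as written. What remains is that the route is never tied to the endpoint, an overnight low on a continuously worn oximeter could be reported at the morning call, and the reference for the fall is absent whichever device is used.

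**Unseen forms may hold the rule.** The Follow-up Questionnaire, the set-up forms and the content of the Enrollment Eligibility Form are not shown. They might carry a reading rule or a baseline value, so a reader should not infer that none exists anywhere. The endpoint definition should still state it.

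**Less desaturation in OSA patients may be real benefit.** Aim 2 suggests that CPAP could treat respiratory distress in these patients. That is fair, and it is another reason to call the bias conditional.

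**The percentages depend on chosen inputs.** They do, and halving the OSA share shows how strongly. They cannot be read as estimates of this trial's error rate.

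**The table in Protocol 10.2 mainly sorts adverse events for reporting.** Agreed: it does not establish a rival primary endpoint. Its wording still differs from Protocol 1.3 under a Clinical Endpoints heading, and the sections need reconciling.

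**Aim 2 is exploratory, and an adjusted model would be imprecise.** Both are true. Imprecision should be reported; it does not make an unadjusted comparison answer the question of independent impact.

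**Conclusion.** The point holds in a limited form and should be fixed. On the documents alone, the >4% component cannot be scored without choosing a reference, and the choice matters: a reading of 92 changes status between references of 96 and 97. Also on the documents alone, the wording does not confine either saturation component to call-time oximeter values.

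The possible advantage to CPAP from sleep readings requires that overnight or WatchPAT values be counted. Its size is unknown, and with call-time values only and no overnight lows reported it is absent. The false-positive figures are illustrations on assumed inputs, and the conclusion does not depend on them.

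The Aim 2 mismatch stands separately. Two unadjusted comparisons cannot give the independent impact of factors that the protocol itself expects to be correlated. The 20.0% figure is likewise only an illustration.

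**What to change.** **Endpoint (Protocol 1.3 and SAP General Design Issues).**
1. State that both saturation components use the pulse-oximeter value current at the scheduled check-ins to 72 hours, by the same rule in both arms. State that WatchPAT and overnight-low values do not count in the primary endpoint; they may be reported as a sensitivity analysis.
2. Name one pre-randomization reference for the >4% fall, such as the ER saturation.
3. That value may be absent (Protocol 2.3 includes patients denied entry to the ER) or taken on supplemental oxygen. In either case do not assess the >4% component, and say explicitly that this is not a missing primary outcome under the SAP's failure rule. Death, admission or ED visit, and saturation below 90 still apply. Report the number of such patients by arm.
4. State how check-in windows before equipment delivery are handled, so that they are not scored as failures.
5. Reconcile Protocol 10.2 with Protocol 1.3 and the SAP on whether the symptom condition applies to the endpoint.

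**Aim 2 (SAP Exploratory Analyses).** Add one exploratory logistic model in the control arm with OSA and obesity entered together, for the primary endpoint, reported with confidence intervals.

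**Cost.** Wording and one model, with no new visits. There will be fewer saturation events, so a lower composite rate, and some genuine nocturnal desaturation will not be counted. The ER reference comes from another device and may be older in patients already discharged, which adds noise. The two-covariate model will be imprecise, with the interval of about 0.33 to 3.05 shown above on assumed inputs.
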